1.0 Objectives

- Assess the effect of morning bright light versus dim light therapy (control) on fatigue and sleep continuity disturbance in lung cancer survivors.
- Predict efficacy to morning bright light therapy versus dim light therapy (control) on fatigue and sleep continuity disturbance in lung cancer survivors.
- Evaluate, in a preliminary way, the extent to which time from treatment (as a proxy iatrogenic effects), sleep homeostatic “de-prime” (mismatch between sleep opportunity and ability), and circadian factors (phase and amplitude) predict illness severity and treatment response.

1.1 Hypothesis

Hypothesis 1: Subjects in the Bright Light Treatment group will exhibit significant improvements as compared to Dim Light Treatment in fatigue, sleep and circadian activity rhythms.

Hypothesis 2: Subjects typed during baseline as having circadian dysrhythmia using actigraphy (circadian phase and amplitude abnormalities) will be significantly more likely to exhibit treatment responses.

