3.0 Inclusion and Exclusion Criteria

3.1 Describe the criteria that define who will be included or excluded in your final study sample.

Fifty-two lung cancer survivors with sleep continuity disturbance will be recruited over 2 years. Eligibility criteria include the following: age >21 , stage I-III, non-small cell lung cancer, ≥ 6 weeks and ≤ 3 years post-surgical resection who are medically and psychiatrically stable. Subjects must be able to give consent. An NCI-designated comprehensive cancer center with a well-established thoracic surgery practice will be the recruitment site. A collaborative recruitment arrangement in the past has resulted in successful recruitment goal achievement.

3.2 Describe how individuals will be screened for eligibility.

The PI or research assistant (RA) will screen all eligible participants for sleep apnea using the ApneaLink device. Participants who screen positive for sleep apnea will receive 2 printed reports of the ApneaLink results: one for themselves and a copy for their provider, who will be advised to refer the participant for further sleep evaluation. Following a negative screen for sleep apnea, participants will be evaluated for sleep continuity disturbance through the use of Insomnia Severity Index, Epworth Sleepiness Scale and 14-day sleep diaries. Participants will also be screened for circadian activity rhythm disturbance with 14-day actigraphy and Morningness-Eveningness Questionnaire. A folder will be provided with each of the pretreatment instruments to complete and an actigraph to wear 24/7 at home. Following completion of pretreatment measures, participants will be randomized using a random number assignment to either red-yellow (control dim light) versus blue-green (experimental bright light) directed light therapy. Participants will be trained on how to wear the directed light therapy for 60-minutes within 30-minutes upon awakening for 1-week (Redd et al., 2014).

3.3 *Indicate specifically whether you will include or exclude each of the following special populations: (You may not include members of these populations as subjects in your research unless you indicate this in your inclusion criteria.)*

- *Adults unable to consent*
- *Individuals who are not yet adults (infants, children, teenagers)*
- *Pregnant women*
- *Prisoners*

These populations will not be included in the study.

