8.0 Study Endpoints

8.1 *Describe the primary and secondary study endpoints.*

The primary endpoint is whether subjects have a significant improvement in self-reported fatigue, sleep and circadian rhythms with the bright light intervention as compared to the dim light intervention. The secondary endpoint is to determine whether pre-treatment subjects with circadian dysrhythmia (circadian phase and amplitude abnormalities) will be significantly more likely to exhibit treatment responses than those who were not identified as having circadian dysrhythmia.

8.2 *Describe any primary or secondary safety endpoints.*

Response: It is expected that some patients with stage I-III NSCLC may experience periods of low oxygenation during sleep that may be identified during screening with the ApneaLink. We added a letter of referral to give to patients who may wish to alert their Providers about this finding.

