after treatment. Treatment adherence and safety will be evaluated by self-report start/end time on sleep diaries and with weekly telephone/text reminders.

9.3 Describe procedures performed to lessen the probability or magnitude of risks.

Weekly telephone calls will be negotiated and utilized to identify Adverse Events and adherence, in addition to self-report adherence on sleep diaries.

9.4 Describe all drugs and devices used in the research and the purpose of their use, and their regulatory approval status.

Response:

- **Direct Light Therapy** - Re-Timer is a directed light device, worn like a pair of glasses that produces a 100% UV-free red-yellow (dim light-control) or blue-green (bright light-experimental), which may improve sleep and reset circadian rhythms. Regulatory status: classified as a wellness device (no FDA classification as medical device)
- **ApneaLink** – ApneaLink is a compact, lightweight, portable device used for overnight screening for sleep apnea, providing information about respiratory effort, pulse, oxygen saturation, nasal flow and snoring. Regulatory status: approved (FDA)
- **Actigraphy (Ambulatory Monitoring, Inc., Ardsley, NY)** – is a wrist worn device that uses a piezoelectric sensor that generates a signal based on movement. The analog signal is then digitalized and for each 1-minute epoch an activity count is calculated and stored. Software application allow for objective sleep-wake patterns (total sleep time, sleep latency, wake after sleep onset, number of awakenings, sleep efficiency) and circadian activity rhythm assessment (mesor, amplitude, acrophase, etc.). Regulatory status: approved (FDA)

9.5 Describe the source records that will be used to collect data about subjects. (Attach all surveys, scripts, and data collection forms.)

- **Demographics and Treatment Survey:** A general demographics questionnaire used to assess personal (age, gender), lifestyle (smoking history and current use of tobacco, stimulants, and alcohol), disease (stage and type of lung cancer) and treatment (schedule, type and dose of chemotherapy, other medications used and side effects) factors.
- **Functional Assessment of Chronic Illness Therapy Fatigue (FACIT) (Cella, Lai et al. 2011)** – The FACIT Measurement System is a part of a collection of quality of life questionnaires targeted to the management of chronic illness. FACIT has 13-items with a 5-point Likert scale with well established validity and reliability to assess fatigue.

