11.0 Data Management

11.1 Describe the data analysis plan, including any statistical procedures.

Hypothesis testing will be conducted using 2x2 ANOVAs for the first specific aim, with Logistic Regressions for the second specific aim (predicting treatment response and non-response) and with Linear and Logistic Regressions for the third specific aim (predicting illness severity and treatment response).

11.2 Provide a power analysis.

Response:

The primary outcome for sleep is the sleep efficiency score. Previous research has indicated that persons with satisfactory sleep have a sleep efficiency score exceeding 85, whereas persons reporting unsatisfactory sleep have a score at most 70, with both groups reporting a standard deviation of approximately 15. The estimated effect size from this study

is 1. The goal of this study is to improve sleep efficiency from an unsatisfactory level to a satisfactory level. Using a large effect size of .08 with a one-tailed significance of .025 and power of 80%, the required sample size for the two-group comparison is 26 per group for a total sample of 52.

11.3 Describe the steps that will be taken to secure the data (e.g., training, authorization of access, password protection, encryption, physical controls, certificates of confidentiality, and separation of identifiers and data) during storage, use, and transmission.

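### Hypothesis 2 tests a yes/no circadian type with no stated cut-off, although the actigraphy phase and amplitude behind it are continuous and could be used directly

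*Combined protocol and SAP*

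**What the plan says.** Section 1.1 expects "Subjects typed during baseline as having circadian dysrhythmia using actigraphy (circadian phase and amplitude abnormalities") to respond more often to treatment. Section 8.1 makes this the secondary endpoint: such participants "will be significantly more likely to exhibit treatment responses than those who were not identified as having circadian dysrhythmia". The comparison is therefore between two groups.

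The measures behind the type are numeric. Section 9.4 says that the actigraph software gives "circadian activity rhythm assessment (mesor, amplitude, acrophase, etc".). Section 3.2 places the assessment before randomization: "Participants will also be screened for circadian activity rhythm disturbance with 14-day actigraphy and Morningness-Eveningness Questionnaire". No section gives a threshold, a reference norm, a rule for combining phase and amplitude, or the person who assigns the type.

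Section 11.1 plans the analysis "with Logistic Regressions for the second specific aim (predicting treatment response and non-response"), without saying how the predictor is coded. For the third aim it plans to proceed "with Linear and Logistic Regressions for the third specific aim (predicting illness severity and treatment response"). Section 1.0 describes that aim as a preliminary look at whether factors including "circadian factors (phase and amplitude) predict illness severity and treatment response". No yes/no type is mentioned there, but the coding is again unstated.

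**The concern.** A logistic regression takes a continuous predictor as it stands. Reducing acrophase and amplitude to a type treats a participant just past the cut like one far past it, and a participant just short of it like one far short. In a sample of 40 to 52 that is a material loss of power for the secondary endpoint.

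The protocol's own preliminary work (2.2) related acrophase itself, not a type, to quality-of-life scores.

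The missing rule has a second consequence. Two investigators following the protocol exactly could type the same participants differently, and a later trial could not reproduce the split. Recording at baseline fixes when the data are taken. It does not fix the rule that turns them into yes or no.

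**Working it through.** **The plan's own figure.** There is none for Hypothesis 2. The only sample size, 26 per group (11.2), is for sleep efficiency. It reproduces with an exact t-test at one-sided 0.025 if the printed .08 is read as 0.8 (power 80.7%). It has no bearing on this point.

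**Inputs.** From the documents: 52 participants (9.1, 11.2) and 40 completers (23.2). Assumed: one roughly normal marker, a linear effect, and a proportion p on one side of the cut. The documents give no value for p.

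**Information kept by a split.** The share retained is φ(z_p)² / [p(1−p)], where φ is the standard normal density and z_p the p-quantile.

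- p = 0.50: 0.3989² / 0.25 = 0.637, loss 36.3%
- p = 0.30: 0.3477² / 0.21 = 0.576, loss 42.4%
- p = 0.25: 0.3178² / 0.1875 = 0.539, loss 46.1%
- p = 0.20: 0.2800² / 0.16 = 0.490, loss 51.0%

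With 40 completers the effective number is 40 × 0.637 = 25.5 down to 40 × 0.490 = 19.6. With 52 it is 33.1 down to 25.5.

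**Outside those assumptions.** At p = 0.15 the loss is 57%, and at p = 0.10 it is 66%. If the type means abnormal on either of two independent markers, the loss against their equally weighted sum is about 53% (half typed) to 67% (one fifth typed). If the true relation is a threshold, or runs in both directions of phase, the formula does not apply.

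**What this means for power (illustration).** Assume a correlation of 0.4 between marker and response on the continuous scale, 40 completers and a two-sided 5% test.

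- Continuous, 1 df: arctanh(0.4) × √37 = 2.577, so power is Φ(2.577 − 1.96) = 73%.
- Median split: arctanh(0.4 × √0.637) × √37 = 2.012, power 52%.
- One-fifth split: arctanh(0.4 × √0.490) × √37 = 1.750, power 42%.
- Continuous, joint 2-df test with only one marker informative: noncentrality 2.577² = 6.64 against the critical value 5.99, power 63%.

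Simulated logistic tests (log odds ratio 0.9 per SD and about 40% responders, both assumed) agree. At n = 40, power is 69-74% continuous against 47-51% for a median split; at n = 52 it is 81-83% against 64-66%.

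**If the cut were chosen after responses are seen (upper case).** With no true association, 40% responders and at least 20% on each side, searching one marker for its best cut gives a false-positive rate of about 26-30% (n = 20 to 52) against a nominal 5%. Searching two independent markers gives about 46-51%.

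**The case against.** **Phase abnormality may run both ways.** This is the strongest objection. Sections 1.1 and 8.1 speak of abnormalities without a direction, and a linear acrophase term tests only whether a later peak predicts response. In a simulated two-sided case (abnormal beyond 1 SD either way, odds ratio about 6, both assumed), the linear term has about 8% power at n = 40 and n = 52. The matching yes/no type has 72% and 83%. The documents lean the other way: 2.2 reports more phase delay and weaker rhythmicity in poor sleepers and links later acrophase to poorer quality of life, and 2.3 cites phase-delayed acrophase. The objection does not rescue an undefined split, but it does mean that direction must be stated before a linear term is used.

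**The third aim already covers this.** It names phase and amplitude as predictors of response. A reader might infer that the plan as a whole throws away 36-51% of its circadian information. The documents do not support that, because of this aim and because the range rests on assumptions they do not state. However, the aim is preliminary and its coding is unstated, and the secondary endpoint still rests on the type.

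**Nobody plans a post-hoc cut.** This stands. A reader might infer from the monthly review of cumulative data (12.6), with efficacy outcomes among the data reviewed (12.2), that the split will be tuned to the responses. But 1.1 and 3.2 place typing at baseline, before randomization, and 12.6 names only correction of coding and entry errors as the outcome of review. The inflated error rates describe what an unlocked rule permits, not what is proposed.

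**Two continuous markers create multiplicity.** Tested separately at 5%, they give 1 − 0.95² = 9.75% if independent. This stands, and the fix must deal with it.

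**It is a pilot.** That limits the weight of the point. It does not make a coarser predictor preferable.

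**Conclusion.** The point holds for Hypothesis 2 and the secondary endpoint. Even if followed exactly, the plan tests a coarsened predictor whose definition is not given. The loss is about 36-51% of a marker's information, provided that the marker is roughly normal, its effect is monotone and linear, and 20-50% of participants fall on one side. It can be larger for a more extreme cut or an either-marker rule, and the calculation fails for a threshold or two-directional effect.

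The protocol does not say whether Hypothesis 2 uses both arms. The fraction lost is the same either way, but with about 20 bright-light completers the split would leave the information of only about 10 to 13 (20 × 0.490 = 9.8; 20 × 0.637 = 12.7).

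The risk of a data-driven cut is a reason to lock the rule, not a finding about the investigators' intentions. Overall this is a cheap improvement worth making. It does not affect the primary comparison.

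**What to change.** In 1.1, 8.1 and 11.1:

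- Make baseline acrophase and baseline amplitude, entered as continuous variables in one logistic model, the only predictors for Hypothesis 2.
- Judge the hypothesis by a single joint 2-df test, or state another multiplicity rule in advance.
- State beforehand which direction of phase counts as abnormal. The background points to delay. If both directions count, replace the linear phase term by deviation from a pre-stated reference.
- Keep any typed group for description only, with its cut-offs and combining rule fixed from baseline data before any post-treatment data are viewed.

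The cost is wording in three places, with no new data. The main test would no longer yield a simple yes/no patient label, a functional form must be assumed in advance, and power could fall if the true relation is a threshold. The joint test also gives back part of the gain when only one marker matters: 63% against 73% for a single continuous marker in the illustration above, though still above the 52% of a median split on that marker.

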2.0 Background

2.1 *Describe the relevant prior experience and gaps in current knowledge.*

Fatigue and sleep disturbance are common in cancer survivors (Berger et al., 2009; Roscoe et al., 2007; Pachman et al., 2012). Fatigue is reported in up to 97% of patients receiving cancer treatment and in 34% of cancer survivors (Goedendorp et al., 2013; Kapo et al., 2015). Sleep disturbance is reported in up to 88% of patients receiving cancer treatment and 56% of cancer survivors (Ancoli-Israel, 2009; Barsevick et al., 2010; Berger et al., 2009; Palesh et al., 2010). When compared to other patients diagnosed with cancer, patients with lung cancer have more than double the prevalence of fatigue and sleep disturbance (Davidson et al., 2002; Gooneratne et al., 2007).

The assessment of fatigue is common in cancer research. Less common is the evaluation of sleepiness and sleep disturbance. While related, these three phenomena may have distinct etiologic pathways and require (or best respond) to different treatment approaches. Fatigue refers to mental and physical weariness and exhaustion, where performance is compromised. Sleepiness is identical to fatigue with one critical difference: patients are also vulnerable to falling asleep at inappropriate times and places. Sleep disturbance is a generic term for all sleep complaints and disorders including sleep continuity disturbance (i.e., difficulty falling and staying asleep), respiratory disturbance during sleep (e.g., sleep apnea and nocturnal hypoxia/hypoxemia), and/or motor disturbances during sleep and parasomnias. For this study, sleep disturbance will specifically refer to sleep continuity disturbance (SCD) and respiratory disturbance (RD) during sleep.

The rather singular focus on cancer related fatigue and the assumption that this occurs with cancer treatment, suggests that fatigue should abate either with the response to, and discontinuation of, treatment. As noted above, this is largely true for fatigue (~60% reduction from treatment to survivorship) but less true for sleep disturbance (30% reduction from treatment to survivorship). In both cases significant, the survivorship prevalence is high and is comparable to, or exceeds, the population general population rates. The lack of resolution in both cases suggests that additional treatment is necessary, particular during survivorship. The question is “where and how to follow-up?” In the absence of mature data on sleepiness in cancer survivors, the higher prevalence rates of sleep disturbance suggests that this may be the best first therapeutic target. Given, a large literature on circadian rhythm disturbance in cancer patients and survivors (Golombek et al., 2013), this suggests that chronobiologic treatments in general, and Bright Light Treatment (BLT) in particular is an ideal option.

Preliminary testing of BLT has been conducted in a variety of cancer patients to improve cancer-related fatigue, but not in patients with lung cancer. Additionally, the efficacy of BLT on improving sleep continuity disturbances, daytime functioning and quality of life has not been assessed in lung cancer survivors. Accordingly, we proposed to conduct a preliminary study of the effects of BLT in patients who are lung cancer survivors.

2.2 Describe any relevant preliminary data.

The multidisciplinary team assembled for this project has conducted three studies that involved lung cancer survivors (ref). These studies established that lung cancer survivors (n=76) experienced middle insomnia (i.e. difficulty maintaining sleep) and determined that patients receiving

chemotherapy for lung cancer (n=50) had early (i.e. difficulty falling asleep) and middle (difficulty staying asleep) insomnia (Gooneratne, Dean et al. 2007, Dean, Finnell et al. 2010). Our most recent mixed method, longitudinal study with 4 measures over 6-months (n=29) found that 89% reported the occurrence of fatigue and 67% reported fatigue was persistent across treatment. In addition, poor sleepers (72%) had less activity, weaker rhythmicity and more phase delay compared to good sleepers before and during treatment for non-small cell lung cancer. Acrophase, where peak activity in a 24-hour period occurs, was significantly negatively related to FACT-L physical and functional subscales and total scores indicating later peak activity is related to poorer QOL. These findings support the occurrence of fatigue, sleep continuity disturbance and circadian activity rhythm disturbance in lung cancer survivors and support for the rationale for testing BLT.

2.3 Provide the scientific or scholarly background for, rationale for, and significance of the research based on the existing literature and how will it add to existing knowledge.

The guiding theory for this proposal is the Two-Process Model of Sleep Regulation, a leading theory of sleep regulation (Borbely 1982). It suggests that sleep occurs when the homeostatic drive to sleep (process S) approaches an upper threshold, and awakening from sleep occurs when process S reaches a lower threshold. The need to sleep increases the longer you are awake. The second process, process C, is a sinusoidal rhythm that fluctuates across the 24-hour day and is driven by a clock-like mechanism in the brain (suprachiasmatic nuclei). The circadian system communicates time of day (light and dark cues from the retina) and thereby regulates the transition from wakefulness to sleep and the transition from sleep to wakefulness. For example, in an individual awake during the day and sleeping at night, the circadian process C is highest from 3am to 5am, when it is very difficult to overcome the need to sleep and is lowest from 4pm to 6pm, where sleep propensity is minimal. The circadian process C and the homeostatic process S both contribute to sleep consolidation. The interaction between these two processes forms the basis for a remarkably standardized period of sleep at night and a consolidated period of wakefulness throughout the day. However, mechanisms that oppose or enhance process S or process C can have a significant effect on the timing, duration and structure of sleep as well as daytime functioning.

In the context of cancer and cancer survivorship, the question is “are one or both of these processes” altered by the disease, its treatment, or by strategies adopted by patients to cope with and/or manage their fatigue and sleep disturbance. Homeostatic dysregulation may occur as a result curtailed time awake during the day and increased time in bed at night. The trigger for these behavioral changes (which de-prime sleep homeostasis) may be the patient’s sense of fatigue (which may occur with

the disease process or as a result of treatment) and signal to the patient that they need more sleep when what they are experiencing is fatigue and not sleepiness. The end result is a mismatch between sleep ability and sleep opportunity and that this results in sleep continuity disturbance, daytime sleepiness, and an exacerbation of extant daytime fatigue. Circadian dysregulation may also occur because of altered sleep wake schedules and/or to changes in how much and when the patient is exposed to bright light (Berger and Farr 1999, Berger, Farr et al. 2007, Ancoli-Israel, Rissling et al. 2012). Further, the circadian system may be dysregulated owing to intrinsic factors. Cancer, or its treatment, may directly alter core body temperature rhythms or amplitude, suppress, enhance or phase shift melatonin secretion, and/or fundamentally alter and dysregulate other neuroendocrine functions that have a circadian periodicity and influence fatigue, sleepiness, and sleep (Armaiz-Pena, Cole et al. 2013).

Most cancer research on fatigue (and to a lesser extent sleepiness and sleep disturbance) has focused on circadian dysregulation. To date it has been found that cancer patients exhibit circadian rhythm desynchronization of cortisol and melatonin (Dogliotti, Berruti et al. 1990, Dolberg, Hirschmann et al. 1998, Davis, Mirick et al. 2001), disrupted phase-delayed activity acrophase (Ancoli-Israel, Rissling et al. 2012, Berger, Hertzog et al. 2012), lower circadian quotient (Levin, Daehler et al. 2005, Berger, Hertzog et al. 2012) and that cancer survivors exhibit flattened biomarkers of circadian rhythms (Bower, Ganz et al. 2005, Bower 2006, Bower, Ganz et al. 2006, Bower 2007, Bower, Ganz et al. 2007). These data strongly suggest that circadian factors are associated with fatigue and sleep-wake disturbances (Levin, Daehler et al. 2005) and that chronobiologic interventions may be useful for the management of cancer related fatigue, sleepiness, and/or sleep disturbance (Ancoli-Israel, Rissling et al. 2012, Berger, Hertzog et al. 2012, Redd, Valdimarsdottir et al. 2014). Circadian rhythm disturbances are managed according to the specific type of disorder, but three common therapies are briefly discussed: Chronotherapy, Melatonin Therapy, and Bright Light Therapy.

Chronotherapy is a behavioral intervention to progressively re-align one's biologically based and preferred sleep phase with standard clock time (Eckerberg, Lowden et al. 2012). Melatonin Therapy entails the administration of exogenous melatonin (melatonin is also a neurohormone produced in the pineal gland) to exert chronobiotic effects (Burgess, Savic et al. 2003, Burgess and Fogg 2008, Burgess, Revell et al. 2008). That is, melatonin is used to produce phase shifts in the biological clock. These shifts, like those produced with chronotherapy, are used to re-align one's biologically based and preferred sleep phase with standard clock time. Bright Light Therapy uses an environmental cue to phase advance or phase delay circadian rhythms. Bright light therapy (BLT) has been shown to be effective in reducing sleep and circadian rhythm disturbances associated with a variety of disorders (e.g. jet lag, seasonal affective disorder, depression, delayed or advanced sleep phase and other sleep

disorders). Preliminary testing of BLT has been conducted in a variety of cancer patients to improve cancer-related fatigue, but not in patients with lung cancer. Additionally, the efficacy of BLT on improving sleep continuity disturbances, daytime functioning and quality of life has not been conducted with lung cancer survivors. Of the previously mentioned therapies, the proposed BLT delivered via eye mask may increase compliance, since the mask can be aimed directly at the eyes and treatment requires minimal effort. Light masks may be a more energy-efficient (through the use of only eight LEDs) and portable method, compared to traditional light boxes.

2.4 Include complete specific citations/references.

Ancoli-Israel, S., P. J. Moore and V. Jones (2001). "The relationship between fatigue and sleep in cancer patients: a review." Eur J Cancer Care (Engl) 10(4): 245-255.

Ancoli-Israel, S., M. Rissling, A. Neikrug, V. Trofimenko, L. Natarajan, B. A. Parker, S. Lawton, P. Desan and L. Liu (2012). "Light treatment prevents fatigue in women undergoing chemotherapy for breast cancer." Support Care Cancer 20(6): 1211-1219.

Armaiz-Pena, G. N., S. W. Cole, S. K. Lutgendorf and A. K. Sood (2013). "Neuroendocrine influences on cancer progression." Brain Behav Immun 30 Suppl: S19-25.

Berger, A. M. and L. Farr (1999). "The influence of daytime inactivity and nighttime restlessness on cancerrelated fatigue." Oncol Nurs Forum 26(10): 1663-1671.

